**RISE Primary Outcome Analysis Plan – Pediatric Medication Study**  
**Approved by RISE Steering Committee, Sept 2017**  
**Approved by RISE DSMB, November 2017**

Often the Disposition Index (DI) – insulin sensitivity \* insulin response – is used as an overall measure of beta-cell function that appropriately accounts for the reciprocal relationship of insulin sensitivity and the beta-cell's insulin response. In these analyses, the DI assumes that the product of the two variables is constant within an individual at a given time, such that changes in insulin sensitivity would be mirrored by a proportional change in the insulin response. This implies that all points along the line represent the same level of metabolic function. In many instances this relationship has been demonstrated using insulin responses to be a rectangular hyperbola (by definition, the slope of the log-log relationship equal to -1.0); however, in others this relationship has just been assumed. The power calculations for RISE were based on the DI using data provided by several investigators that used methodologies that differed from those used in RISE.

During protocol development there was thus concern that relationships underlying this constant depend on the actual measures of peptide (insulin or C-peptide) release by the beta cell. In particular, the slope of the log-log relationship between secretion and sensitivity might not be equal to -1.0 for the C-peptide measures chosen for RISE as had been observed in prior studies based on insulin measures. Therefore, the protocols specifically state that the primary outcomes would be based on two different C-peptide responses (steady state and maximal) adjusted for insulin sensitivity defined as the glucose disposal rate divided by steady state insulin (aka M/I) during the hyperglycemic clamp. However, given the likely possibility that the relationship may not be a rectangular hyperbola, the protocol did not specify details of the approach to be used for the primary outcome analysis as a decision would be based on evaluation of the baseline data.

During analysis of the baseline data, we found that the DI (i.e. sensitivity x secretion) is sometimes paradoxically lower in pediatric participants than adult participants, despite the fact that the insulin sensitivity vs. C-peptide curves describing the relationship between these two variables appears higher in children. This contradictory finding is at least in part due to the fact that the range of values for insulin sensitivity among children is narrow compared to that of adults, i.e., children are more insulin resistant than adults. Further, the log-log slopes of insulin sensitivity vs. C-peptide responses are not equal to -1 in children or adults (or overall). Although the untransformed data show a clear inverse relationship typical of a hyperbolic curve, the slopes for each of the primary outcome measures on the log scale is approximately -0.3 (not -1.0 as may have been expected); this is a hyperbola but not a square hyperbola. Thus, the approach of performing the primary outcome analysis comparing treatment groups after washout, with a test of difference in DI at Month 15 adjusted for baseline, may not be appropriate and needed to be reassessed.

Several options were considered including a simple linear regression model (on a log scale) of C-peptide (and insulin) release as a function of insulin sensitivity, with a term for treatment group and adjusting for both variables at baseline. However, this was also deemed inappropriate because that model would estimate the difference in C-peptide (and insulin) release between groups assuming that there was no difference in insulin sensitivity between groups. Rather, we want to account for movement of both variables simultaneously without forcing a specific relationship between them. This can be accomplished by performing the primary outcome analysis using two separate models: insulin sensitivity at Month 15 vs. treatment arm (adjusted for baseline) and C-peptide (and insulin) release at Month 15 vs. treatment arm (adjusted for baseline), where the two models are fit simultaneously using Seemingly Unrelated Regression techniques. This provides an

estimate of the treatment group difference in insulin sensitivity as well as the treatment group difference in the release of the beta-cell peptides, while allowing for the correlation among the insulin sensitivity and peptide release measures. This yields an estimate of the joint covariance structure of the two models, and allows a joint statistical test of both variables using a 2-DF chi-square test of the treatment arm difference in each model. Thus, we will be able to test whether both the insulin sensitivity and C-peptide (and insulin) release variables are different across treatment groups at Month 15, adjusted for their baseline value.

This approach will provide a clear answer to the question of whether the Month 15 result differs by treatment, adjusting for baseline measures. However, given that an underlying reciprocal relationship is expected, it is possible that a significant difference could be found between groups, but that this represents a proportional shift without a specific improvement in peptide release adjusted for sensitivity. In other words, the data points could lie on a different part of a shared relationship curve such that the change represents a mutually compensated change in these terms without a separate underlying change in beta-cell function. Therefore, if the results of the two-model analysis are significant, further analysis will evaluate the patterns of change in either or both variables within each group.

Below is sample Primary Outcome R code for this primary analysis.

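### Does replacing the DI comparison with a 2-DF joint test leave the primary analysis with less power than was planned?

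*SAP*

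**What the plan says.** The SAP's first paragraph defines the Disposition Index as the product of insulin sensitivity and insulin response, and says that "power calculations for RISE were based on the DI using data provided by several investigators that used methodologies that differed from those used in RISE". The second paragraph explains that "the protocol did not specify details of the approach to be used for the primary outcome analysis as a decision would be based on evaluation", meaning an evaluation of the data collected at baseline.

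The third paragraph gives the result of that evaluation: "the slopes for each of the primary outcome measures on the log scale is approximately -0.3 (not -1.0 as may have been expected"). It concludes that the primary comparison by "a test of difference in DI at Month 15 adjusted for baseline, may not be appropriate and needed to be reassessed".

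The fourth paragraph adopts two baseline-adjusted Month 15 models, one for sensitivity and one for peptide release, fitted together by seemingly unrelated regression. The fit "allows a joint statistical test of both variables using a 2-DF chi-square test of the treatment arm difference in each model", and the sample R code carries this out. The SAP gives no power, sample size, detectable effect or alpha for either test.

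**The concern.** The endpoint, the degrees of freedom and the source data behind the power calculation all differ from the analysis now planned. A 2-DF chi-square test has a higher critical value than a 1-DF test (5.99 against 3.84 at the 5% level), so an unchanged signal is harder to detect. The baseline data needed for a new calculation were already being analysed when the SAP was written, yet the SAP reports none. If power had really dropped by several points, a non-significant result could be read as stronger evidence of no effect than the test supports.

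**Working it through.** The SAP has no power figure to reproduce, so the check asks whether changing the test must lower power.

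**Inputs.** From the SAP: a log-log slope of about -0.3 (third paragraph), read as the slope of C-peptide on sensitivity; DI as a product, so log DI is the sum of the two logs; and the 2-DF joint test. Assumed: two-sided alpha 0.05; DI-test power of 80%, 85% or 90%; a ratio *k* of the C-peptide SD to the sensitivity SD of 0.5, 0.75 or 1.0; the baseline slope describes the Month 15 covariance; baseline adjustment ignored.

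**Step 1: equal noncentrality.** For 80% power the 1-DF noncentrality is (1.960 + 0.842)² ≈ 7.85. A noncentral chi-square with 2 DF and that value gives 70.9%. Starting from 85% and 90%, the results are 77.0% and 83.5%. Restoring 80% needs a noncentrality of 9.63, and 9.63/7.85 ≈ 1.23, or about 23% more information. At alpha 0.025, 80% becomes 70.7%. This arithmetic is correct, but it holds the noncentrality fixed, not the treatment effect.

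**Step 2: equal effect.** Let d = (effect on log sensitivity, effect on log C-peptide) and let S be their covariance matrix, up to a common scale.

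- DI test: λ₁ = (1′d)² / (1′S1)
- Joint test: λ₂ = d′S⁻¹d

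By the Cauchy-Schwarz inequality (1′d)² ≤ (1′S1)(d′S⁻¹d), so λ₂ ≥ λ₁ always. They are equal only when d is proportional to S1. Step 1 therefore describes the worst case for the joint test. With the DI test at 80%, the joint test is the more powerful one whenever λ₂/λ₁ exceeds about 1.23.

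**Step 3: numbers.** With the sensitivity variance set to 1, S has diagonal (1, k²) and off-diagonal -0.3. Then 1′S1 = 1 + k² - 0.6 and det S = k² - 0.09. For an effect on C-peptide alone, d = (0, 1), with k = 1:

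- λ₁ = 1/1.4 = 0.714
- λ₂ = 1/0.91 = 1.099
- ratio = 1.538, so the joint noncentrality is 7.85 × 1.538 ≈ 12.07 and the power is 88.5%

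Joint-test power where the DI test has 80% (λ₂/λ₁ in brackets):

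| Effect (sensitivity, C-peptide) | k = 0.5 | k = 0.75 | k = 1.0 |
|---|---|---|---|
| C-peptide only (0, 1) | >99.9% (4.062) | 95.7% (2.037) | 88.5% (1.538) |
| Sensitivity only (1, 0) | 71.6% (1.016) | 77.0% (1.146) | 88.5% (1.538) |
| Equal on both (1, 1) | 94.0% (1.879) | 75.3% (1.101) | 70.9% (1.000) |
| Along the slope (1, -0.3) | 83.2% (1.327) | 95.0% (1.964) | 99.3% (2.857) |
| Proportional to S1 | 70.9% (1.000) | 70.9% (1.000) | 70.9% (1.000) |

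For a shift of (1, -1), log DI does not change. The DI test then rejects only at its alpha level, while the joint test can still detect the shift.

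**Step 4: what the SAP claims.** It mentions the DI-based power calculation once, with its weakness attached, and never applies it to the joint test. No sentence in the document is contradicted by the table.

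**The case for a change.** The strongest reply is that an unknown direction makes a restatement more useful, because joint power anywhere from 70.9% to over 99% leaves a null result hard to read. Nor is all of the extra power relevant. The joint noncentrality is the sum of a sensitivity part and a part for C-peptide adjusted for sensitivity. For a shift along the curve the adjusted part is zero, yet the joint test gains power, and the SAP's fifth paragraph concedes that such a shift need not mean better beta-cell function. For an effect on C-peptide alone, the joint and adjusted noncentralities coincide, so against the adjusted 1-DF contrast the fall from 80% to 70.9% is exact.

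The algebra stands, but it changes the comparator. The planned power was for the DI, not for a sensitivity-adjusted contrast, and the SAP's fourth paragraph rejects a sensitivity-adjusted regression as the primary model and gives its reason. The fifth paragraph deals with the compensated shift by examining the pattern of change once the joint test is significant. It also stands that detectable effects for the joint test are not written here. A SAP commonly leaves these to the protocol, which is not at hand. Stating them would alter no test, estimate, sample size or decision rule. A null result would be judged mainly on the estimated arm differences and their precision, and the model supplies both.

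**Conclusion.** The concern does not hold. The power calculation and the primary test do rest on different quantities, but the SAP says so itself and explains that the method was deliberately left open. That the change of test lowers power at the same effect is not established. With the DI test at 80%, the joint test has between 70.9% and over 99.9% power in the cases examined, and the lower figure applies only to one direction of effect. An effect on C-peptide alone gains power at all three assumed SD ratios; an effect on sensitivity alone loses at two and gains at one. The need for about 23% more information belongs to the same worst case.

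The figures assume two-sided alpha 0.05, the SAP's slope of -0.3 applied to the Month 15 covariance, SD ratios of 0.5 to 1.0 and no baseline adjustment. The inequality behind the conclusion needs none of these assumptions. What is left is a wish for extra detail, not an error in the plan.

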#### R code and sample output for primary outcome with Seemingly Unrelated Regression model using systemfit

```
> fit12=systemfit(list(Eq1 = log_mi ~ Treatment + log_mi_base,
                      Eq2 = log_cpeptide_steady ~ Treatment +
                          log_cpeptide_steady_base),
                  method='SUR',
                  data=RISEM15)

> linearHypothesis(fit12, test = "Chisq",
                  c('Eq1_TreatmentTreat2=0', 'Eq2_TreatmentTreat2=0'))
```

Hypothesis: Eq1\_TreatmentTreat2 = 0      Eq2\_TreatmentTreat2 = 0

Model 1: restricted model

Model 2: fit12

	Res.Df	Df	Chisq	Pr(>Chisq)
1	xxx			
2	xxx-2	2	xxxx	x.xxx ← pvalue for the 2-DF joint statistical test of both sensitivity and secretion variables of the treatment arm difference

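### Does the SAP need a rule for reading the two primary joint tests (steady-state and maximal C-peptide) together?

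*SAP*

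**What the plan says.** The second paragraph of the SAP attributes the primary outcomes to the protocol: "the primary outcomes would be based on two different C-peptide responses (steady state and maximal"), each adjusted for M/I from the hyperglycemic clamp. It adds that "the protocol did not specify details of the approach to be used for the primary outcome analysis". The paragraph on the baseline data uses the plural again ("the slopes for each of the primary outcome measures on the log scale") and concludes that the Disposition Index comparison, "with a test of difference in DI at Month 15 adjusted for baseline, may not be appropriate and needed to be reassessed".

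The replacement consists of "performing the primary outcome analysis using two separate models: insulin sensitivity at Month 15 vs. treatment arm (adjusted for baseline"), plus a matching model for release. The two are fitted by seemingly unrelated regression, which "allows a joint statistical test of both variables using a 2-DF chi-square test of the treatment arm difference in each model". The sample R code shows one such pair, with "Eq2 = log_cpeptide_steady ~ Treatment" as the release equation. The only conditional step comes just before the code: "if the results of the two-model analysis are significant, further analysis will evaluate the patterns of change".

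**The concern.** A 2-DF test that contains the M/I treatment term has room for only one release term. Two primary C-peptide responses therefore imply at least two joint p-values. The SAP does not say whether one significant result is enough, whether both are needed, in what order they are read, or at what level.

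If the two runs disagreed, a reader of the SAP alone could not say whether the primary outcome had been met. A rule picked after the Month 15 results were seen would be data-dependent, and the lenient choice (either test at full level) would exceed a nominal 5%. The joint test was also adopted after the baseline data had been examined, so one might doubt that a rule written for the Disposition Index still applies. The trigger for the follow-up analysis could look equally unsettled.

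**Working it through.** **What can be reproduced.** The SAP gives no alpha, sample size, effect size or power figure. The one number to check is the 2 DF. It agrees with the code, which sets two restrictions to zero: the treatment term for M/I and the treatment term for one release measure.

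**Inputs for the error rates (all assumed, none from the SAP).**
- 0.05 per joint test.
- Asymptotic z-statistics *z*0 (M/I), *z*1 (steady state) and *z*2 (maximal).
- Correlation *a* between M/I and each C-peptide contrast, base value -0.45, range 0 to -0.6. The SAP's log-log value of about -0.3 is a slope, not a correlation.
- Correlation *r* between the two C-peptide contrasts.

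**Formula.** For response *j*, Q*j* = (*z*0² - 2*a* *z*0 *z*j + *z*j²)/(1 - *a*²), compared with the 2-DF chi-square cutoff: -2 ln(0.05) = 5.99 at 0.05, and -2 ln(0.025) = 7.38 at 0.025.

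**Type I error under no effect anywhere, *a* = -0.45, 1,000,000 draws.**

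| *r* | Either at 0.05 | Both at 0.05 | Holm, overall 0.05 |
|---|---|---|---|
| 0.3 | 8.07% | 1.99% | 4.12% |
| 0.5 | 7.87% | 2.19% | 4.04% |
| 0.7 | 7.43% | 2.62% | 3.81% |
| 0.9 | 6.52% | 3.53% | 3.34% |
| 0.99 | 5.52% | 4.54% | 2.77% |

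Check: P(either) + P(both) must equal 0.05 + 0.05 = 0.10. At *r* = 0.7, 0.0743 + 0.0262 = 0.1005, which agrees within simulation error. Over all values of *a*, the either-test rate runs from 5.5% to 8.1%. A separate simulation with *a* of -0.3, -0.5 and -0.7 and *r* of 0.5 to 0.9 gave 6.4% to 8.1% for either and 1.9% to 3.6% for both. The independence figure, 1 - 0.95² = 9.75%, does not describe this design, because both tests share the M/I term.

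**Where a false positive can arise.** Each joint null says that M/I and one C-peptide response are both unaffected. If treatment changes M/I, both joint nulls are false and neither test can produce a type I error. The multiplicity question therefore concerns only the case of no M/I effect.

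**Disagreement and power** (assumed effect of 2.5 SE on both responses, none on M/I, *a* = -0.45, *r* = 0.5/0.7/0.9).
- Exactly one test significant: 31/23/13%.
- At least one rejected, uncorrected: 86/83/77%.
- At least one rejected, Holm: 78/74/68%.
- Both significant at 0.05: 56/59/64%.
- One uncorrected test alone: 71%.

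Holm and both-required each hold the level. They differ in power and in what a positive result means.

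**What the protocol left open.** The sentence containing "the protocol did not specify details of the approach to be used for the primary outcome analysis" gives as its reason that the relationship may not be a rectangular hyperbola, and says the decision would rest on the baseline data. Baseline slopes can inform how release is adjusted for sensitivity. They say nothing about how to combine two p-values. The sentence is therefore no evidence that the protocol lacks a multiplicity rule.

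**The follow-up criterion.** It refers to a two-model analysis, that is, M/I with one response. Applied pair by pair, it tells the analyst what to do when one pair is significant and the other is not.

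**The case for a change.** The strongest case for a change is that this SAP creates the two joint tests. Any protocol rule was written before they existed, and the SAP promises a clear answer on treatment differences at Month 15. Disagreement is not remote either: under the assumptions above it occurs in 13% to 31% of trials in which both responses truly respond. Two sentences would close the matter.

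Part of this stands. The SAP neither states nor cites a rule, and a pointer to the protocol would have helped. The phrase about C-peptide and insulin release also leaves it a little loose whether insulin adds further tests, so two is a minimum count.

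The step from there to a defect does not stand. Bonferroni, Holm and both-required rules work on p-values from any valid test, so replacing the Disposition Index comparison by a joint test does not void a rule for the same two outcomes. The SAP never says that either test suffices, and that is the only reading considered here that inflates the error. The split and power figures depend on an assumed effect size and assumed correlations, not on anything the trial states.

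**Conclusion.** No change to the plan follows. The observation is accurate: there are two primary C-peptide responses, the joint test takes one of them at a time, and the SAP has no sentence on reading the two p-values together. But the SAP states no wrong rule and contradicts nothing. It is a short account of the analysis approach with no design constants, and it attributes the outcome pair to the protocol, where the overall level and any multiplicity rule commonly sit. Analysts would ordinarily run the test once per response, report both, and apply the protocol's rule.

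The possible harm is conditional and moderate: about 5.5% to 8.1% instead of 5% if either test were accepted at an assumed 0.05, and none if both were required. Choosing between Holm and both-required is a trade-off, not a correction. The conclusion rests on the SAP alone. Whether the protocol contains such a rule could not be confirmed here, and all error rates depend on the assumed level and correlations.

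### The 2-DF joint test shows that at least one of the two variables differs between arms, not that both do, and the within-group follow-up cannot say which

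*SAP*

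**What the plan says.** The narrative part of the SAP sets up two baseline-adjusted models, one for insulin sensitivity and one for peptide release, fitted together by SUR. The fit gives an "estimate of the treatment group difference in insulin sensitivity as well as the treatment group difference in the release of the beta-cell peptides". It also "allows a joint statistical test of both variables using a 2-DF chi-square test of the treatment arm difference in each model". From this the SAP concludes: "we will be able to test whether both the insulin sensitivity and C-peptide (and insulin) release variables are different across treatment groups".

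The section with R code and sample output shows the restriction that is tested: "c('Eq1_TreatmentTreat2=0', 'Eq2_TreatmentTreat2=0". The sample output has Df = 2.

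The next paragraph of the narrative says the approach answers whether the Month 15 result differs by treatment. It warns that a significant result may mean that "this represents a proportional shift without a specific improvement in peptide release adjusted for sensitivity". For that reason, if the two-model result is significant, "further analysis will evaluate the patterns of change in either or both variables within each group". No other step after a significant result is stated.

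**The concern.** There are two linked faults.

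First, the conclusion drawn from the test does not match the hypothesis that is coded. Rejecting the null that both coefficients are zero supports only the statement that they are not both zero. One variable may differ and the other not.

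Second, the only stated follow-up does not fill the gap. An evaluation within each arm is not a comparison of arms. The SUR fit does produce a between-arm estimate for each variable, but the SAP attaches no test, interval, order or decision rule to these estimates.

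What is at stake is attribution. After a positive primary result the plan has no stated rule for saying whether insulin sensitivity, C-peptide release or both differ between treatments. A change seen in one arm and not in the other could be reported as a treatment effect on C-peptide when there is none. By the SAP's own account the protocol left the details of the primary analysis open, so this document is where the rule belongs.

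**Working it through.** **1. The two hypotheses side by side.** Let b1 be the treatment coefficient for log M/I and b2 that for log C-peptide.

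| | Null | Conclusion on rejection |
|---|---|---|
| As coded | b1 = 0 and b2 = 0 | b1 ≠ 0 or b2 ≠ 0 (at least one) |
| As described | b1 = 0 or b2 = 0 | b1 ≠ 0 and b2 ≠ 0 (both) |

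A test of the second row requires each 1-df test to reject. The SAP gives no sample size, alpha, SD or effect size, so it has no figure to reproduce. Df = 2 agrees with the two restrictions in the code.

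**2. How far apart the two readings are.** Assumptions, none from the SAP: two-sided alpha 0.05; a true effect of 3.24 standard errors on one variable (about 90% power in its own 1-df test); zero effect on the other; correlation ρ between the two estimates. The joint statistic is noncentral chi-square on 2 df with λ = d′R⁻¹d. For d = (3.24, 0) this is λ = 3.24²/(1 − ρ²) = 10.50/(1 − ρ²). The critical value is 5.991.

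| ρ | λ | 2-DF test rejects | Both 1-df tests significant | 2-DF rejects, neither 1-df test does |
|---|---|---|---|---|
| 0 | 10.50 | 83.5% | 4.5% | 0.2% |
| -0.3 | 11.54 | 87.0% | 4.3% | 1.4% |
| -0.5 | 14.00 | 92.8% | 3.9% | 3.9% |
| -0.7 | 20.58 | 98.7% | 3.3% | 7.3% |

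At ρ = 0 the fourth column can be done by hand: 0.90 × 0.05 = 0.045. The joint powers agree with 400,000 bivariate-normal draws to within 0.1 percentage points.

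A full two-equation SUR simulation (3,000 runs per cell, residual correlation -0.3, effect 0.7 SD on one variable only) gives joint rejection of about 72%, 88% and 96% at 30, 45 and 60 per arm. With no effect on either variable it gives 6.2%, 5.9% and 5.4%, close to nominal.

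**3. What the within-group step can do.** Suppose C-peptide does not differ between arms, and suppose the within-group evaluation is done with paired significance tests. The SAP does not say that it is. If each arm's test has probability p of significance and the arms are independent, exactly one arm is significant with probability 2p(1 − p). For no change, p = 0.05 gives 2 × 0.05 × 0.95 = 9.5%. The maximum is 50%, at p = 0.5.

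A simulation (4,000 replicates per cell) conditions this on a significant joint test. Assumed inputs: unit-SD log variables, baseline coefficient 0.6, cross-correlations -0.3, M/I arm difference 0.5 SD, C-peptide arm difference 0, and the same C-peptide change in both arms. The cells give the percentage of significant trials in which exactly one arm shows a significant C-peptide change.

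| Common change (SD) | N = 60 | N = 80 | N = 100 |
|---|---|---|---|
| 0 | 11.8% | 11.2% | 10.8% |
| 0.2 | 38.2% | 42.4% | 45.8% |
| 0.3 | 51.2% | 51.9% | 47.5% |
| 0.4 | 47.4% | 35.7% | 21.4% |
| 0.5 | 28.2% | 14.8% | 5.2% |

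The joint test rejects in 61–62%, 74–75% and 84–85% of trials at the three sizes. These are correct rejections, because M/I does differ. In the same significant trials the between-arm 1-df test for C-peptide rejects in 6.2% to 8.6%.

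**4. A rule that does attribute.** With two hypotheses, the joint null is their intersection. Testing it first at alpha and then each coefficient at the same alpha is a closed procedure, so familywise error is held within one SUR fit. Under the global null (6,000 replicates, N = 60 to 80) the simulated familywise error is 0.046 to 0.055. The joint test can reject when neither single test does. With both effects at 1.5 standard errors in the same direction and ρ = -0.6, λ = 2 × 1.5²/(1 − 0.6) = 11.25. The joint test then rejects in 86% of trials, and in 30% of those neither single test does.

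**5. What no part of this settles.** The SAP reports that "the slopes for each of the primary outcome measures on the log scale is approximately -0.3". A pure shift along that slope, with equal log-scale standard errors assumed, has effects 3.24 and -0.3 × 3.24 = -0.97. The joint test rejects it in 83.5% to 92.4% of trials over the same correlations.

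**The case against.** The strongest reply is that *both* is loose wording for *both tested together*. The preceding sentence and the code output each call it a joint test. The next paragraph claims only that the Month 15 result differs, and the follow-up speaks of either or both variables, so the authors probably knew the distinction. That reading is possible and limits the harm. It does not remove the fault: the sentence is introduced as the conclusion that the test supports, and as written it names a different hypothesis.

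A second reply is that the within-group step is aimed at the compensated-shift question, not at which variable differs, and that the between-arm estimates are already planned. Both statements are fair. They leave the plan with estimates but no rule for using them, and with a follow-up that does not compare arms on any question.

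Third, the percentages for the within-group step measure a practice that the SAP does not prescribe. This stands: they illustrate a risk and do not describe the plan.

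Fourth, single-variable tests do not isolate beta-cell function. A shift along the curve could lead to a C-peptide claim. This also stands, and it is why the SAP's caveat must stay.

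**Conclusion.** The concern holds. The SAP gives the 2-DF test a property it lacks, and its stated follow-up cannot show which variable differs between arms. This rests on the text alone. The test, its code and its p-value are not in question.

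The size is illustrative only. With a true effect on one variable, the joint test rejects in 83.5% to 98.7% of trials, against 3.3% to 4.5% for a rule that requires both. If within-arm significance tests were used, exactly one arm would show a significant C-peptide change in 5% to 52% of significant trials with no arm difference. The between-arm test would reject in 6% to 9%. Sample size, alpha, effects, correlations and the use of within-arm tests are all assumed. The interpretation and follow-up should be corrected, but the primary test need not change.

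**What to change.** 1. Reword the conclusion to say that the test addresses whether at least one of insulin sensitivity and C-peptide release differs between arms.
2. Report each between-arm treatment coefficient with its confidence interval.
3. After a significant 2-DF test, test the treatment coefficient in each equation separately at the same level. Claim a difference in a variable only if its own test rejects, and in both only if both reject. If neither rejects, report only that the pair differs.
4. Label the within-group patterns as descriptive.
5. Keep the warning about a compensated shift, because the 1-df tests do not resolve it. A confirmatory statement about release relative to sensitivity would need its own prespecified contrast.

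The error control applies within one SUR fit. The SAP names "two different C-peptide responses (steady state and maximal) adjusted for insulin sensitivity" as the basis of the primary outcomes, and multiplicity across those two is a separate matter.

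The cost is a few sentences and two 1-df tests from the fit already planned, with no extra data and no alpha cost within that fit.
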